## **Protocol Synopsis**

Study Title	Visual Attention to Text and Pictorial Food Labels: An Eye Tracking Experiment
Funder	National Heart, Lung, and Blood Institute (NHLBI)
Clinical Phase	NA
Study Rationale	

• Adults in the US consume excessive sodium, added sugars, and saturated fats, leading to high rates of hypertension, type 2 diabetes, and heart disease.

• Structural factors like targeted marketing of unhealthy foods, price barriers, and low use of Nutrition Facts labels contribute to worse dietary outcomes among Latino populations.

• Front-of-package (FOP) food labels, especially "high-in" labels (e.g., "High in sugar"), are a promising policy solution to reduce purchase of unhealthy foods.

• Visual elements like icons and graphics in FOP labels may be more effective for Latino and limited English proficiency populations by improving noticeability and comprehension.

• However, it's unknown how different types of FOP labels affect visual attention, message effectiveness, and understandability among Latino and limited English proficiency populations.

Study Objective(s)	The primary objective of this study is to examine attention elicited by different types of FOP sodium labels (i.e., FOP sodium label types) among adults identifying as Hispanic or Latino/a/é (hereinafter Latino).  Primary 

• To evaluate whether intervention FOP sodium labels elicit higher dwell time on the FOP sodium label than control messages.

 Secondary 

• To evaluate whether intervention FOP sodium labels elicit higher levels of 3 secondary outcomes (fixation count on the FOP sodium label, self-reported attention to the FOP sodium label, and perceived message effectiveness of the FOP sodium label), compared to the control.

• To evaluate whether (1) self-reported attention to the FOP sodium label, (2) perceived message effectiveness of the FOP sodium label, and (3) how understandable the FOP sodium label was differs by label type.

Study Design	Within-participants randomized experiment.
Subject Population key criteria for and Exclusion:	
Inclusion Criteria
 

1. Age 18 and older

2. Self-identifies as Hispanic or Latino

 
Exclusion Criteria

---

	
 
3. Less than 18 years old
 
4. Does not identify as Hispanic or Latino
 
5. Has one of the following conditions: (Wears bifocals, glaucoma, permanently dilated pupils, eye implants [artificial lenses, not contact lenses], less than 2 eyes, or blindness)
 

Number of Subjects	~60
Study Duration	Each subject's participation will last approximately 30 minutes. The enrollment period is expected to last ~4 months.
Study Phases	
There are two phases:
 
 
(1) Screening: screening for eligibility and obtaining consent and
 
(2) Intervention: study intervention/experimental treatment.
 

Efficacy Evaluations	
The primary outcome is the amount of time spent looking at the FOP sodium label (i.e., dwell time). This outcome will be measured using eye tracking technology. The secondary eye tracking outcomes are 1) number of times looking at the FOP sodium label (i.e., fixation count), 2) time to first fixation on the FOP sodium label, and 3) dwell time on “natural” claim.
 
Other secondary outcomes include: 1) self-reported attention to the FOP sodium label, assessed with 1 item for each label type adapted from Nonnemaker et al. 2010, 2) perceived message effectiveness of the FOP sodium label, assess with 3 items for each label type, adapted from Baig et al. 2019, and 3) how understandable the FOP sodium label was, assessed with 1 item for each label type, adapted from Brewer et al. 2019. Response options for all measures will range from 1 (low values) to 5 (high values).

Statistical and Analytic Plan	We will evaluate the impact of FOP sodium label types on primary and secondary outcomes using separate mixed effects linear regression models for each outcome, accounting for repeated measures.
	
Primary outcome
 
 
• We will run a mixed effects linear regression model, regressing dwell time on an indicator variable for FOP sodium label type. The control label will serve as the reference group, and the intercept will be treated as random.
 
 
Secondary outcomes
 
 
• We will use pairwise comparisons to compare predicted means for the three intervention FOP sodium label types. The same modeling approach will be applied to secondary outcomes. We will correct for multiple tests using the Benjamini-Hochberg method, treating each outcome as a family of tests and controlling the false discovery rate at 0.05.
 

---

---

**Data and Safety  
Monitoring Plan**

- The principal investigators are responsible for data quality management and ongoing assessment of safety.

---

## **Introduction**

The primary objective of this study is to examine attention elicited by different types of front-of-package (FOP) sodium labels (i.e., FOP sodium label types) among adults identifying as Hispanic or Latino.

## **Study Protocol**

Participants will complete a randomized experiment programmed using Tobii Lab Pro software and Qualtrics. After providing informed consent, participants will view images of cans of soup with 4 different labels (a text-only sodium label, an icon and text sodium label, a pictorial and text sodium label, and a control barcode label). Participants will view each label in a random order. An eye tracker will be used to measure amount of time spent looking at the front-of-package sodium label (i.e., dwell time) (primary outcome) and secondary outcomes: number of times looking at the front-of-package sodium label (i.e., fixation count), time to first fixation on the front-of-package sodium label, and dwell time on “Natural” claim. After viewing all labels, participants will use Qualtrics to rate each label for the remainder of secondary outcomes: self-reported attention to front-of-package sodium label, perceived message effectiveness of front-of-package sodium label, and understandability of front-of-package sodium label.

## **Statistical Considerations**

### **General Principles**

We will use a two-sided critical alpha of 0.05 to conduct all statistical tests. We will use complete case analysis to handle any missing data in analyses of the primary and secondary outcomes.

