### **Primary Outcome**

Primary outcome: Amount of time spent looking at the FOP sodium label (i.e., dwell time). This outcome will be measured using eye tracking technology.

*Hypothesis 1.* We predict that each of the three intervention FOP sodium label types will elicit higher dwell time on the FOP sodium label compared to the control. We predict that the pictorial FOP sodium label will elicit higher amounts of dwell time than the icon label, the icon label will elicit higher amounts than the text-only label, and the pictorial label will elicit higher amounts than the text-only label.

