### **Secondary Outcomes**

Eye tracking secondary outcomes: 1) number of times looking at the FOP sodium label (i.e., fixation count), 2) time to first fixation on the FOP sodium label, and 3) dwell time on “natural” claim.

*Hypothesis 2.* We predict that each of the three intervention FOP sodium label types will elicit higher levels of the 3 secondary eye-tracking outcomes (fixation count on the FOP sodium label, self-reported attention to the FOP sodium label, and perceived message effectiveness of the FOP sodium label), compared to the control. We predict that the pictorial FOP sodium label will elicit higher amounts of these outcomes than the icon label, the icon label will elicit higher amounts than the text-only label, and the pictorial label will elicit higher amounts than the text-only label.

Other secondary outcomes: 1) self-reported attention to the FOP sodium label, assessed with 1 item for each label type adapted from Nonnemaker et al. 2010, 2) perceived message effectiveness of the FOP sodium label, assessed with 3 items for each label type, adapted from Baig et al. 2019, and 3) how understandable the FOP sodium label was, assessed with 1 item for each label type, adapted from Brewer et al. 2019. Response options for all measures will range from 1 (low values) to 5 (high values).

*Hypothesis 3.* We predict that each of the three intervention FOP sodium label types will elicit lower levels of two outcomes (time to first fixation on the FOP sodium label and dwell time on the “natural” claim), compared to the control. We predict that the pictorial FOP sodium label will elicit lower amounts of these outcomes than the icon label, the icon label will elicit lower amounts than the text-only label, and the pictorial label will elicit lower amounts than the text-only label.

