#### 1. Analyses of the primary outcome:

- a. We will run a mixed effects linear regression model, regressing dwell time on an indicator variable for FOP sodium label type. The control label will be the reference group. The model will treat the intercept as random. We will use pairwise comparisons to compare predicted means for the three intervention FOP sodium label types to each other.

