#### 2. Analyses of the secondary outcomes:

- a. We will use the same modeling approach used in the primary outcome to examine the impact of FOP sodium label type on secondary outcomes.

For analyses of primary and secondary outcomes, we will use the Benjamini-Hochberg method to correct for multiple tests. These analyses will treat each outcome as a family of tests, correcting for the six tests within each outcome and controlling the false discovery rate at 0.05.

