### **Exclusions and Outliers**

We do not expect any outliers on survey measures because the Likert-style response options are constrained. We do not plan to exclude outliers for eye tracking outcomes, as is typical for eye tracking studies.

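### Time to first fixation has no defined value when a label is never looked at; on the natural reading, complete-case analysis drops those viewings from this one secondary outcome

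*Combined protocol and SAP*

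**What the plan says.** Study Protocol lists "time to first fixation on the front-of-package sodium label" among the secondary eye-tracking outcomes. Hypothesis 3 (Secondary Outcomes) predicts that each intervention label will produce "lower levels of two outcomes (time to first fixation on the FOP sodium label and dwell time on the “natural” claim), compared to the control", with a further ordering among the three intervention labels.

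Four rules bear on how this outcome would be analysed:

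- Missing data (General Principles): "We will use complete case analysis to handle any missing data in analyses of the primary and secondary outcomes".
- Model (Analyses of the secondary outcomes): "We will use the same modeling approach used in the primary outcome to examine the impact of FOP sodium label type on secondary outcomes". That is a linear mixed model in which, for the primary outcome, "The model will treat the intercept as random". Statistical Methods gives each outcome its own model.
- Multiplicity: Benjamini-Hochberg within each outcome, "correcting for the six tests within each outcome".
- Extreme values (Exclusions and Outliers): "We do not plan to exclude outliers for eye tracking outcomes, as is typical for eye tracking studies".

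No section says what value a never-fixated viewing takes, when it would be censored, how long each image is shown, or whether viewing is fixed or self-paced.

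**The concern.** Never looking at a label is a response to that label, but it produces no time. Dwell time and fixation count have a natural zero for a label that is ignored; time to first fixation does not. A very late first look would stay in the model, because extreme values are kept, while no look at all would most naturally be treated as missing and removed.

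The comparison would then no longer use all four randomly ordered viewings of each participant, but only those in which the label was seen. Being seen happens after randomisation and may depend on the label. At stake is the time-to-first-fixation part of Hypothesis 3: its contrasts could be weakened, or could answer a narrower question than the one stated.

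**Working it through.** **Plan's own figures.** The plan gives no non-fixation rate, latency or viewing time, so there is no figure to reproduce on this point. From Sample Size Needs I use only 60 participants and 4 labels: 60 × 4 = 240 viewings.

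**Assumptions (mine, for illustration only).** A fixed viewing window common to all labels, scaled to W = 1. Non-lookers are slow lookers: their first look would have come after W. The control is missed more often than the label.

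**Step 1: closed form.** Let latency be exponential and p the share never fixated, so the rate is −ln(p).

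- Complete-case mean = 1/rate − p/(1 − p)
- Capped mean (non-looks set to W) = (1 − p)/rate
- Unrestricted mean (viewing continues until everyone looks) = 1/rate

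Take p = 0.10 for control (rate 2.303) and p = 0.02 for the label (rate 3.912).

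| | Control | Label | Difference |
|---|---|---|---|
| Complete-case | 0.434 − 0.111 = 0.323 | 0.256 − 0.020 = 0.235 | 0.088 |
| Capped | 0.9/2.303 = 0.391 | 0.98/3.912 = 0.251 | 0.140 |
| Unrestricted | 0.434 | 0.256 | 0.179 |

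The complete-case difference is 1 − 0.088/0.140 = 37% below the capped one and 1 − 0.088/0.179 = 51% below the unrestricted one. The capped difference is itself 1 − 0.140/0.179, about 21-22%, below the unrestricted one.

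**Step 2: simulation.** 2,000,000 draws; log-normal person effect (log SD 0.5, mean 1); latency exponential or log-normal (log SD 0.8); label latency 0.7 or 0.5 of control; control mean solved for the assumed non-fixation rate. The ranges span these choices.

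| Assumed control non-fixation | Complete-case below capped | Capped below unrestricted |
|---|---|---|
| 1% | 9-13% | 4-6% |
| 10% | 29-41% | 26-32% |
| 20% | 37-53% | 41-51% |

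With the planned random-intercept model fitted, the 10% entry in the middle column is 27-39%.

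**Step 3: viewings lost.** At 10% control non-fixation, 0.10 × 60 = 6 control viewings drop out, about 12 of 240 overall. If complete case means dropping the whole participant, about 10 of 60 are lost.

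**Step 4: the opposite assumption.** If not looking is unrelated to speed, the latency difference among lookers is off by 0-1% in the same simulation framework, so there is no latency bias. The question still changes. Suppose labels that are seen are found after 2 s on average whichever label it is, the window is 5 s, and 10% of control and 5% of label viewings have no look. The complete-case difference is then 0, whereas the capped difference is (0.05 − 0.10) × (5 − 2) = −0.15 s.

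**The case against.** The strongest reply is that the harm depends on facts the plan does not contain. Nothing says a non-look is coded as missing, so its removal is an inference. Hypothesis 1 predicts that "each of the three intervention FOP sodium label types will elicit higher dwell time on the FOP sodium label compared to the control"; that concerns time spent looking, not the share who never look. So the documents do not establish that the control is missed more often. Bias also requires non-lookers to be slow lookers, and Step 4 shows it vanishes otherwise. Latency among lookers is a coherent quantity, while a capped mean blends speed with whether the person looked. All of this stands, and it is why the point is stated conditionally.

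A reader might infer from Step 1 that the planned analysis loses about half of the true latency effect and that capping would recover it. The documents do not support that: the rates are assumed, and the capped difference is a separate, window-restricted quantity that also falls well short of the unrestricted one. The fairer comparison is complete-case against capped, and even that compares two estimands.

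A reader might also infer that the complete-case rule is wrong in itself, or that the primary outcome is compromised. Neither follows. The rule suits tracking failure, and dwell time has a natural zero for a label not looked at, although the plan does not state that coding.

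What does not stand is the view that this is mere missing detail. The stated rules, followed as written, most naturally remove viewings because of how the participant responded. If the rule is left open, the choice among dropping, capping and censoring would be made with the data in hand.

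**Conclusion.** The gap is real and confined to one secondary outcome, which the synopsis objectives do not name. Separate models and within-outcome multiplicity correction keep it from affecting other results, and the sample size is untouched.

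Its size cannot be computed from the documents and is negligible if non-fixation is rare. The 29-41% shrinkage relative to capping rests on 10% control non-fixation, a common fixed window and slow non-lookers. Under those conditions the direction is toward no difference, so the likely cost is a missed effect, not a false claim of benefit. The plan should be amended before analysis; confidence is medium because the non-fixation rate and its relation to speed are unknown.

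**What to change.** In General Principles and in the secondary-outcome analysis section, for time to first fixation only:

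1. State whether viewing time is fixed or self-paced, and its length if fixed.
2. State that a never-fixated viewing with valid tracking is not missing data.
3. Right-censor it at the end of that viewing in a time-to-event model with participant clustering. Only if viewing time is fixed and common to all labels, the alternative is to set it to the viewing duration in the planned mixed model.
4. Report the proportion of viewings with a fixation by label, and latency among lookers as a descriptive result.
5. Keep complete-case handling for tracking failure or absent recordings, and state that a no-look viewing scores 0 for dwell time and fixation count.

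The cost is a few sentences, with no new participants or measures. Self-paced viewing additionally needs each viewing's duration. There are trade-offs: a capped estimate mixes speed with whether the person looked, and with self-paced viewing censoring assumes that viewing length carries no information about latency, so viewing length should be reported by label. The power of the censored model has not been worked out here.

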### **Primary Outcome**

Primary outcome: Amount of time spent looking at the FOP sodium label (i.e., dwell time). This outcome will be measured using eye tracking technology.

*Hypothesis 1.* We predict that each of the three intervention FOP sodium label types will elicit higher dwell time on the FOP sodium label compared to the control. We predict that the pictorial FOP sodium label will elicit higher amounts of dwell time than the icon label, the icon label will elicit higher amounts than the text-only label, and the pictorial label will elicit higher amounts than the text-only label.

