### **Sample Size Needs**

Respondents will be approximately 60 US adults ages 18+ who identify as Latino. We powered the study to detect an effect size of  $d=0.27$  or larger, assuming 4 repeated measures, 80% power, a correlation among repeated measures of 0.60, and a nonsphericity correction of 1. This effect size is conservative given that our recent meta-analysis found a large effect size for the impact of pictorial (vs. text) warnings on dwell time ( $d=1.74$ ) in eye tracking studies.

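### Do the synopsis and the SAP body need a joint success rule for Hypothesis 1 because they file the dwell-time label ranking differently?

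*Combined protocol and SAP*

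**What the plan says.** **Protocol Synopsis, Study Objective(s).** The single primary bullet concerns labels against control: "To evaluate whether intervention FOP sodium labels elicit higher dwell time on the FOP sodium label than control messages". The secondary bullet on differences between label types covers self-reported attention, perceived message effectiveness and "how understandable the FOP sodium label was differs by label type". It does not mention dwell time.

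**Protocol Synopsis, Statistical and Analytic Plan.** The Primary outcome bullet describes the mixed model and ends with "The control label will serve as the reference group, and the intercept will be treated as random". The Secondary outcomes bullet opens with "We will use pairwise comparisons to compare predicted means for the three intervention FOP sodium label types", then says that the same modelling approach will be used for the secondary outcomes.

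**Primary Outcome, Hypothesis 1.** This predicts that each label exceeds control on dwell time, then adds a ranking of the labels, beginning "We predict that the pictorial FOP sodium label will elicit higher amounts of dwell time than the icon label" and going on to icon over text and pictorial over text.

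**Analyses of the primary outcome (item 1).** The same model is followed by "We will use pairwise comparisons to compare predicted means for the three intervention FOP sodium label types to each other".

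**Analyses of the secondary outcomes (item 2), closing paragraph.** Benjamini-Hochberg at a false discovery rate of 0.05 applies to primary and secondary outcomes alike, "correcting for the six tests within each outcome".

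**The concern.** Read literally, the synopsis gives three primary contrasts and the body gives six. Hypothesis 1 is also one numbered hypothesis made of six predictions, and nothing says whether it stands on the three control contrasts, on all six, or contrast by contrast. If the labels clearly beat the barcode control but differ less from one another, an author could report that the primary objective was met (synopsis) or that the primary hypothesis was only partly supported (body), and could choose between them after seeing the data. Sample Size Needs seems to add to the doubt, because it supports the design with a pictorial-versus-text effect ("our recent meta-analysis found a large effect size for the impact of pictorial (vs. text) warnings on dwell time"), which is a ranking contrast.

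**Working it through.** **Step 1. Which way does the synopsis point?** Three features suggest a misplaced heading rather than a deliberate demotion of the ranking.
- In the synopsis, the pairwise sentence is followed by one extending the same approach to the secondary outcomes. That order makes sense only if the pairwise sentence still describes the primary analysis. It is also the order of items 1 and 2 in the body.
- The objectives list is incomplete in other respects. It omits time to first fixation and dwell time on the natural claim, which the synopsis itself names as secondary outcomes under Efficacy Evaluations. Absence from the bullets is therefore weak evidence of a contrast's status.
- The general objective above the bullets is about attention to the different label types, which is wide enough to include the ranking.

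**Step 2. What does the sample size imply?** Inputs from Sample Size Needs: d = 0.27, m = 4 measures, correlation ρ = 0.60, nonsphericity correction 1, 80% power, N about 60. Assumption: f = d/2 = 0.135.
- Omnibus repeated-measures F test: λ = f²·N·m/(1 − ρ) = 0.018225 × 60 × 4 / 0.40 = 10.9, with 3 and 177 df. Power is 79.2% at N = 60; 80% needs N = 62; the detectable d at N = 60 is 0.273. The plan's figure is reproduced.
- The calculation thus fits a four-condition omnibus test. The cited 1.74 serves only to call 0.27 conservative. Neither shows which contrasts are primary.

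**Step 3. How often would the two readings give different headlines?** Simulation with N = 60, compound symmetry (SD 1, ρ = 0.60), pooled-error contrasts on 177 df, Benjamini-Hochberg at 0.05 over six two-sided p-values, and success counted only in the predicted direction. The documents give no means, so every pattern is assumed.

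| Control / text / icon / pictorial (SD units) | All three control tests | All six | Control tests but not all six |
|---|---|---|---|
| 0 / 0.27 / 0.54 / 0.81 | 62% | 17% | 45% |
| 0 / 0.80 / 1.07 / 1.34 | 100% | 35% | 65% |
| 0 / 0.80 / 1.20 / 1.60 | 100% | 86% | 14% |
| 0 / 0.80 / 1.67 / 2.54 (pictorial minus text 1.74) | 100% | 100% | 0% |

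The first row is not the plan's design effect: Sample Size Needs never says that 0.27 is a step between adjacent conditions. Those means have SD 0.27 × √1.25 = 0.30, so f = 0.30, over twice the 0.135 that reproduces the sample size. At f = 0.135 the last column is about 10% with equal steps (0.135/√1.25 = 0.121 each) and about 44% if the three labels are equal and all above control (by 0.135 × 4/√3 = 0.312).

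**Step 4. What does the last column measure?** It counts trials in which the control contrasts succeed and at least one ranking contrast does not. In the first row the six contrasts succeed singly with probability 62%, 99% and 100% (text, icon and pictorial against control) and 62%, 62% and 99% (icon against text, pictorial against icon, pictorial against text). These figures do not depend on which heading the ranking sits under, because the model, the six-test family and the adjusted p-values are the same.

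**The case for a change.** The best case for a change is that a heading slip does not explain why no objective bullet mentions a dwell-time ranking, that Benjamini-Hochberg leaves the combination of results open, and that two or three sentences would close both gaps. The 1.74 also concerns pictorial versus text only, so it gives no assurance on icon versus text or pictorial versus icon. With a barcode as control, strong control contrasts and weaker ranking contrasts are plausible.

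Most of these facts stand: the synopsis and body differ, no joint rule is written, and a mixed result is quite possible. The inference does not stand. Hypothesis 1 is worded as separate directional predictions, each with its own adjusted test, so contrast-by-contrast reporting is the natural reading. The rule requiring all six appears nowhere in the documents; setting it against the three-contrast reading is what creates the apparent conflict. Labels beating control and a ranking only partly confirmed can both be true of the same data, and a report of all six adjusted results says both.

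**Conclusion.** The inconsistency is real but minor: probably a misplaced heading in the synopsis, together with an incomplete list of objectives. Following the body as written gives six pre-specified, directional, FDR-adjusted conclusions on dwell time, and the choice of reading affects none of them. The frequency of mixed results, from 0% to about 65% over the patterns tried, rests on assumed means and describes how the evidence might fall, not an error in the analysis. A joint success rule would add nothing to the inference in this label experiment. The conclusion rests on all six contrasts being reported individually, as the six-test correction implies. Aligning the synopsis with the body would be tidy, but it is an editorial matter.
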